10.3.1	Pooling Across Centers	10
10.3.2	Pooling Across Protocol Versions at Enrollment	10
10.4	HANDLING OF MISSING DATA.....	11
10.5	OTHER DATA SUMMARIES.....	11
10.6	CHANGES TO PLANNED ANALYSES	11
10.7	STATISTICAL SOFTWARE	11

1 Purpose of the Statistical Analysis Plan

The purpose of this Statistical Analysis Plan (SAP) is to summarize the statistical methodologies being used to confirm the primary effectiveness endpoint and assess the secondary effectiveness, additional effectiveness, and safety endpoints of the immediate implantation of the Straumann® Bone Level Tapered Implant (study device). The SAP will be used should there be any discrepancies with the protocol.

2 Study Design

2.1 Study Design/Overview

This is a post-market, prospective, randomized, controlled, multi-center study with five years of follow-up. The study is being performed at three centers within the United States. A total of 53 subjects were enrolled and randomized with 46 subjects having completed the 12 months post-implant loading (primary endpoint) follow-up. No more than 30 subjects were enrolled per center and subjects were randomized equally to have immediate (test treatment) or delayed (control treatment) implantation.

2.2 Device Description

The Straumann® Bone Level Tapered Implant is used for both the treatment and control groups as the investigation is of the implant timing. The implant is available in three different diameters (3.3, 4.1, and 4.8 mm) and five different lengths (8, 10, 12, 14, and 16 mm). In addition to the implant device, clinicians may also use Straumann® restorative components that are appropriate for the implant.

2.3 Study Schedule

All subjects were screened (Visit 1) for study eligibility within 45 days of the tooth extraction and randomization visit (Visit 2a). Subjects were randomized during the extraction procedure after the tooth had been extracted. Each subject was randomized to have the implantation surgery (Visit 2b) either immediately, on the same day as the extraction (test), or delayed, after 17 weeks from the extraction (control).

Subjects had a first post-operative assessment 10 days after implantation (Visit 3) to assess wound healing and remove sutures. The implant was then uncovered (Visit 4) and loaded (Visit 5) after 10 ± 3 weeks from implantation, which may have been performed at the same visit. An impression for final restoration was taken 5 weeks after implant loading (Visit 6) with the final restoration having been performed 10 weeks after implant loading (Visit 7).

Subjects have had follow-up visits after 6 and 12 (primary endpoint) months from implant loading (Visits 8 and 9 respectively) and will have additional follow-up visits after 24, 36, 48, and 60 months from implant loading (Visits 10, 11, 12, and 13 respectively).

2.4 Study Success

The study will be deemed a success if the change in mean peri-implant marginal bone levels (mesial and distal) from implant loading to 12 months post-loading for the test treatment is no worse than that of the control treatment.

2.5 Randomization and Enrollment

Randomization occurred during the tooth extraction visit immediately after the tooth had been extracted and the inclusion and exclusion criteria had been confirmed. Subjects were enrolled upon randomization.

3 Study Objectives

This study is designed to assess the clinical and radiographic outcomes of using a Straumann® Bone Level Tapered Implant for immediate implantation following extraction of a tooth in the pre-molar and anterior region of the maxilla and mandible (test) compared to the outcomes of placing this implant in healed sites (control). The outcomes that will be compared include the following:

- Change in mean peri-implant marginal bone levels (mesial and distal)
- Implant success and survival
- Buccal bone dimensional change
- Implant stability
- Soft tissue changes
- Subject satisfaction
- Adverse events

4 Effectiveness and Safety Endpoints

4.1 Primary Effectiveness Endpoint

The primary effectiveness endpoint is defined as the change in the mean of the mesial and distal aspect crestal bone levels from implant loading to 12 months post-implant loading.

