5.2.8 Implant Success and Survival

Implant survival will be assessed at all visits following the surgical visit. A surviving implant is an implant that is in place at the time of follow-up.

Implant success will be assessed at implant loading, and at 12, 24, 36, 48, and 60 months post loading. A successful implant will meet all of the following criteria according to Buser¹⁶:

- Absence of persistent subjective complaints, such as pain, foreign body sensation, and/ or dysesthesia
- Absence of a recurrent peri-implant infection with suppuration
- Absence of mobility
- Absence of a continuous radiolucency around the implant

[figure not shown]
Non-surviving implants will be counted as an unsuccessful implant.

Any dental implant showing excessive bone loss, radiolucency, or infection shall be treated in the manner best suited to the well-being of the subject, including treatment to save the dental implant. Continuous radiolucency, implant mobility, and recurrent perimplant infection with suppuration shall be recorded on the adverse event form (see section 7.3.4).

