5.3.2 Early Withdrawal

Any subject may withdraw from the study at any time without prejudice and will be offered an alternative treatment for his/her dental condition. Subjects will be advised of the need for the prescribed follow-up visits for their ongoing care, well-being, and collection of any safety data.

The Investigator may withdraw any subject from the study in the case of:

- Non-compliance with the protocol
- Failure to attend the follow-up visits
- Serious Adverse Event (SAE) or adverse event, which in the opinion of the Investigator prevents the subject's further participation in the study.
- Failure to achieve primary stability if primary stability is not obtained and the implant is removed, the patient will be withdrawn at the time of implant removal.
 No further follow up is necessary.
- No study implant placed if the study implant is never placed, regardless of reason, the patient will be withdrawn. No further follow up is necessary.

The subject withdrawal will be documented on a Study Termination/ End of Study CRF and must include the reason for the subject withdrawal. Efforts should be made to capture the primary study endpoint for each subject prior to withdrawal, if possible. If the subject fails to attend follow-up visits, at least three attempts to reach the subject must be documented; with at least one of the attempts made by certified letter.

Withdrawn subjects will not be replaced.

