6.7 Visit 5 – Implant Loading (BASELINE)

At 10 weeks (± 3 weeks) after implant surgery (2 - 4 weeks after uncovering the implant), and contingent upon good primary stability, the study implant will be loaded with a temporary abutment and restoration in appropriate occlusion. Note that uncovering of the implant (Visit 4) and implant loading can be done at the same visit at the discretion of the investigator.

The subject will have the following procedures and/or evaluations performed and documented:

- Temporary prosthesis seated
- Oral hygiene evaluation

- Concomitant mediation
- Adverse event check
- Implant stability by RFA
- Verbal confirmation of pregnancy status, if applicable
- Standardized periapical radiographs
- CBCT localized
- Implant survival and success
- Intra-oral photographs

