5.1 Sample Size

This is a post-market, prospective, randomized, controlled, multi-center study. The sample size and study duration were determined to allow for adequate healing and the opportunity for comparable changes. In addition, a statistically powered sample size of 28 subjects (14 subjects per treatment group) is required for the primary endpoint. The sample size estimation is based on the following assumptions:

- Subjects are assigned to either the test or control treatment group
- The expected difference between treatment groups is 0 mm
- The standard deviation for both the test and control treatments is 0.5 mm
- A clinically significant difference between treatment groups is ≥ 0.5 mm (non-inferiority margin, δ)
- Testing will use a one-sided t-test having at least 80% power and a 5% significance level

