10.4 Handling of Missing Data

All practical monitoring and follow-up steps will be taken to ensure complete and accurate data collection. All analyses will be based on available data only; no imputation for missing data is planned.

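### Implants that are lost, removed or never loaded get no score in the primary endpoint, so the only deciding non-inferiority test is run on surviving implants

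*SAP*

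**What the plan says.** SAP 4.1 sets the primary endpoint as "the change in the mean of the mesial and distal aspect crestal bone levels from implant loading to 12 months post-implant loading". SAP 5 computes it as the 12-month level minus the loading level, so both films are needed. SAP 2.4 judges study success on this change alone. The primary analysis set is mITT, which keeps everyone who received the study treatment even if they terminate early (SAP 10.1.2).

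On missing values, SAP 10.4 states: "All analyses will be based on available data only; no imputation for missing data is planned". Protocol 8.5.5 foresees a last-observation-carried-forward sensitivity analysis if more than 10% of primary values are missing. The SAP omits it, and SAP 1 says the SAP prevails over the protocol.

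Several routes lead to an implant without a value:

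- **Removal at surgery.** Protocol 5.3.2: "if primary stability is not obtained and the implant is removed, the patient will be withdrawn at the time of implant removal", with no further follow-up.
- **No loading.** Protocol 6.7: "contingent upon good primary stability, the study implant will be loaded with a temporary abutment and restoration". Without loading there is no baseline film and no date from which to count 12 months.
- **Loss** between placement and loading, or between loading and 12 months.

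Protocol 5.2.8 does score such implants for another endpoint: "Non-surviving implants will be counted as an unsuccessful implant". Success and survival are secondary endpoints, summarised without a test (SAP 6).

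**The concern.** A lost implant differs from a missed film: the bone level does not exist because the treatment failed. Dropping it treats the failure as uninformative. In a non-inferiority trial that works in favour of whichever arm fails more often, and immediate placement could be called no worse on its survivors.

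No other planned analysis of the primary endpoint restores these subjects.

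- The ITT analysis also uses available data only.
- The per-protocol set excludes implants that did not reach primary stability, which removes more failures.
- Carrying the last value forward would not help even if reinstated. Protocol 5.2.6 schedules no bone-level film between loading and 12 months, so a lost implant would usually be scored as zero change, and a never-loaded implant has no baseline.

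The direction is not far-fetched. Protocol 1 notes that primary stability can be technically hard to achieve with immediate placement, and the expected-effects table in Protocol 7.2.6 lists early and late loss as probable.

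**Working it through.** **Inputs from the documents.** One-sided t-test at 5%, margin 0.5 mm, expected difference 0, and "The standard deviation for both the test and control treatments is 0.5 mm" (SAP 5.1). 53 randomised and 46 with a completed 12-month visit (SAP 2.1), so 7/53 = 13.2% without one.

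**Assumptions, not in the documents.** 46 scored subjects split 23:23; observed difference 0 among them; the score X given to a lost implant; the number k of losses. Loss is coded positive, so larger values in the test arm are worse.

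**The plan's own figure.** For n per arm the noncentrality is 0.5 / (0.5 × √(2/n)). At n = 14 this is 2.646; with critical value 1.706 on 26 df the power is 82.4%. At n = 13 the power is 79.7%. The stated 14 per arm is reproduced.

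**Survivors only.** U = 0 + 1.680 × 0.5 × √(2/23) = 0.248 mm, below 0.5, so non-inferior.

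**Adding k test losses at X mm.**

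- Mean difference: D = kX / (23 + k)
- Test-arm sum of squares: 22 × 0.25 + 23kX² / (23 + k); control: 22 × 0.25 = 5.5
- Pooled variance: the two sums divided by 44 + k
- U = D + t(0.95; 44 + k) × s × √(1/(23 + k) + 1/23)

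Example, k = 2 and X = 3: D = 6/25 = 0.24. Test sum of squares = 5.5 + 16.56 = 22.06. s = √(27.56/46) = 0.774. Standard error = 0.2236. U = 0.24 + 1.679 × 0.2236 = 0.615 mm.

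| Test losses | Score (mm) | U (mm) | Within 0.5? |
|---|---|---|---|
| 0 | – | 0.248 | yes |
| 1 | 3 | 0.449 | yes |
| 2 | 1.5 | 0.398 | yes |
| 2 | 2 | 0.466 | yes |
| 2 | 2.5 | 0.539 | no |
| 2 | 3 | 0.615 | no |
| 3 | 2 | 0.556 | no |
| 3 | 1.5 | 0.462 | yes |
| 4 | 1.5 | 0.519 | no |

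**Tipping score for two test losses:** about 2.24 mm. It is 2.14 to 2.31 mm for splits from 21:25 to 25:21; 2.45, 1.97 and 1.65 mm for SD 0.4, 0.6 and 0.7; 1.62 mm if the survivors' observed difference is 0.1 mm; and 2.80 mm if it is −0.1 mm.

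**Losses in both arms.** Two per arm at 3 mm: D = 0, s = √(44.12/48) = 0.959, U = 1.677 × 0.959 × √(2/25) = 0.455 mm, which passes.

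**Method.** With two test losses at 3 mm and true difference 0 among survivors, simulation gives a chance of passing of about 20% by the t-test and about 82% by a margin-shifted Wilcoxon test. With no losses the t-test passes about 95% of the time.

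**Sign.** SAP 5 labels a positive change as gain, while SAP 5.2 rejects when test minus control is below +0.5. Read literally, two test losses of 3 mm give −0.24 + 0.375 = 0.135 mm, lower than 0.248, so failures would make passing easier.

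**The case against.** The strongest reply is that the plan does not ignore failures. Survival and success head the list of secondary endpoints, survival is checked at every visit from Visit 3, losses are among the listed adverse device effects, and Protocol 8.1 enrols 14 extra subjects to inform success and survival. That stands: losses will be visible by arm. What is missing is any link between them and the non-inferiority claim.

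A reader might infer that two lost test implants overturn the trial. The documents do not support that. They give no score for a lost implant. The 2.5 mm flag in Protocol 7.3.4 and the worst category of 3 mm in SAP 5 were written for other purposes, and using them here is an assumption. At 1.5 or 2 mm two losses do not change the decision, nor do two per arm at 3 mm.

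Much of the reversal also comes from variance. At 3 mm the mean difference is only 0.24 mm, while the pooled SD rises from 0.50 to 0.77. Protocol 8.4.1 allows a non-parametric method if normality fails, and a rank test is far less sensitive. This objection stands and shapes the fix.

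Nor do the documents show that any of the seven subjects lost an implant; 13.2% is inside the 25% attrition allowance. Protocol 5.3.2 and 8.5.5 ask for the endpoint before withdrawal where possible, so some late losses may yield a film. No passage says that a retained implant stays permanently unloaded. Hence a failed implant normally, but not always, lacks a value.

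**Conclusion.** The point holds as a gap in the plan. No rule scores a lost, removed or never-loaded implant for the primary endpoint, available-data analysis drops it, and the one deciding test then describes surviving implants. Its effect on the decision is conditional. With 23 scored subjects per arm, observed difference 0, SD 0.5 mm and no control losses, two test losses reverse the result only at about 2.2 mm or more each, three at 2 mm and four at 1.5 mm. Whether any of this occurred cannot be told from the documents, because the number, arm and cause of failures are not given. It should be addressed, but the primary test need not be replaced.

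**What to change.** First reconcile the sign in SAP 5 and 5.2, so that greater bone loss in the test arm counts against non-inferiority. Without this any failure score could work backwards. Then keep the available-data t-test as primary and:

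1. Add a category for implants lost, removed or never loaded to the bone-change table, by arm, with all mITT subjects as the denominator.
2. Add a supportive tipping-point analysis that scores these subjects in both arms over a pre-specified range, for example 1.5 to 3 mm loss, with a rank-based version because such scores are outliers for a t-test.
3. State in SAP 2.4 that the non-inferiority conclusion will be reported with losses by arm and the tipping point, and described as applying to surviving implants if it does not hold over that range.

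The cost is SAP wording, one table row and one extra analysis on data already collected. SAP 10.6 allows an amended SAP if it is approved before the primary analysis; after that, the change must be reported as a deviation in the clinical study report. The downside is that the score range is a convention, so the analysis is supportive only.

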4.2 Secondary Effectiveness Endpoints

The five secondary effectiveness endpoints are defined as follows:

- Implant success and survival at 12 months post-implant loading
- Buccal bone dimensional change, measured on cone beam computed tomography (CBCT) images, from implant loading to 12 months post-implant loading
- Implant stability measured by radio frequency analysis (RFA) at implant placement, implant loading, and final restoration
- Gingival and papilla soft tissue change from final restoration to 12 months post-implant loading
- Subject satisfaction of esthetics, function and level of pain at 12 months post-implant loading

4.3 Additional Effectiveness Endpoints

The five additional effectiveness endpoints are each evaluated at 24, 36, 48, and 60 months post-implant loading follow-ups and are defined as follows:

- Change in mean crestal bone levels from implant loading to follow-up
- Implant success and survival at follow-up
- Buccal bone dimensional change from implant loading to follow-up
- Gingival and papilla soft tissue change from final restoration to follow-up
- Subject satisfaction of esthetics, function and level of pain at follow-up

4.4 Safety Endpoints

The safety endpoints are defined as the number of adverse events or adverse device effects experienced and the number and proportion of subjects experiencing an adverse event or adverse device effect throughout the study.

5 Analysis of Primary Effectiveness Endpoint

The primary effectiveness endpoint evaluates the difference in the change in mean crestal bone levels from implant loading to 12 months post-implant loading between the treatment and control groups. The change is defined as the mean crestal bone level of the mesial and distal aspects of the implant at 12

months post-implant loading minus at implant loading and the difference is defined as the change for the treatment group minus the control group.

The mean crestal bone levels at each visit, and the change in mean crestal bone levels will be summarized for each group with the count, average, standard deviation, median, minimum, and maximum. The mean change in crestal bone levels will also be categorized as Gain (>0), No change (0), Loss <1 mm, Loss <2 mm, Loss <3 mm, or loss ≥ 3 mm and summarized with the number and proportion of subjects in each category for each treatment group.

5.1 Sample Size

This is a post-market, prospective, randomized, controlled, multi-center study. The sample size and study duration were determined to allow for adequate healing and the opportunity for comparable changes. In addition, a statistically powered sample size of 28 subjects (14 subjects per treatment group) is required for the primary endpoint. The sample size estimation is based on the following assumptions:

- Subjects are assigned to either the test or control treatment group
- The expected difference between treatment groups is 0 mm
- The standard deviation for both the test and control treatments is 0.5 mm
- A clinically significant difference between treatment groups is ≥ 0.5 mm (non-inferiority margin, δ)
- Testing will use a one-sided t-test having at least 80% power and a 5% significance level

5.2 Primary Analysis

The null hypothesis for the primary analysis is that the difference between the mean change in crestal bone levels for the treatment and control groups is at least the non-inferiority margin (indicating inferior bone gain). Rejection of the null hypothesis indicates the observed data supports the alternative hypothesis that the difference between the mean change in crestal bone levels for the treatment and control groups is less than the non-inferiority margin (indicating non-inferior bone gain). The hypotheses associated with the primary analysis are defined as:

- $H_0: \mu_c - \mu_s \geq \delta$
- $H_1: \mu_c - \mu_s < \delta$

where μ_c is the mean change in crestal bone levels from implant loading to 12 months post-implant loading for the treatment group, μ_s is the mean change for the control group, and δ is the 0.5 mm non-inferiority margin. The hypotheses will be tested using a one-sided t-test with a 5% significance level.

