5.2.6 Marginal Bone Level Changes

Bone level changes will be evaluated on a standardized peri-apical radiograph at implant loading and at 12, 24, 36, 48, and 60 months post-loading. The radiographs will be sent to a centralized location to be evaluated in a blinded fashion by a single reader using a calibrated measuring tool. Additional details will be provided in operations manual to describe how the central radiologist will measure the bone level values from the radiographs.

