7.3.4 ADE Reporting

Adverse device effects must be recorded and submitted to Straumann by completing the AE case report form in the EDC system within five working days of awareness of the event. Safety reporting to the Institutional Review Board (IRB) should occur according to the requirements of the local IRB.

Bone loss reporting: Continuous substantial reduction of the peri-implant bone level is a sign of failure of the implant system. The first European Workshop on Periodontology specified an average marginal bone loss of less than 1.5 mm bone loss within the first year after the insertion of the prosthesis, and thereafter less than 0.2 mm annual bone loss as criteria for measuring success¹⁸. This has been a standard and a basis for success criteria since it was defined in 1993. In a more recent meta-analysis, the authors looked at Straumann implants and determined that a pooled weighted mean of marginal bone level change for Straumann implants was -0.56 mm (95% CI -0.661, -.481) after 5 years. The individual study means of marginal bone level change ranged from -0.15 to -1.0 mm after 5 years.¹⁹ Based on this information the central radiologist will flag any bone level changes that are greater than 2.5 mm in the first year post-loading and any annual changes greater than 1.5 mm in subsequent years. The study manager will review the flagged values and discuss with the principal investigator whether the bone level change will be reported as an ADE.

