8.1 Sample Size

The following assumptions were used to determine the sample size for the primary endpoint of mean change in crestal bone level between implant placement and 12 months postimplant loading:

- Subjects will be assigned to either the test or control treatment group
- The primary analysis is a non-inferiority comparison of the test treatment to the control treatment

- The standard deviation for both test and control treatments is 0.5 mm
- A difference between treatment groups of ≥ 0.5 mm is considered clinically significant (i.e., the non-inferiority margin)
- The difference between the treatment groups is expected to be 0 mm
- Greater than 80% power is considered sufficient
- Statistical test will be performed with a one-sided 5% significance level

The hypotheses associated with the primary endpoint are defined as follows:

$$H_0$$
: $\mu_c \ge \mu_s + \delta$

$$H_1$$
: $\mu_c < \mu_s + \delta$

where μ_c is the mean change in crestal bone level for the test implants, μ_s is the mean change in crestal bone level for control implants, and δ is the pre-defined non-inferiority margin of 0.5 mm. The study will be considered successful if the null hypothesis is rejected, i.e., the conclusion of non-inferiority is achieved. If non-inferiority is achieved at a one-sided α of 5%, a one-side superiority test will be performed at significance level of 5%.

To maintain at least 80% power to detect a difference between treatment groups of 0.5 mm with a common standard deviation of 0.5 mm, 14 subjects per treatment group would be required for a total of 28 subjects. Adjusting for potential 25% attrition, 19 subjects per treatment group will be required for a total of 38 subjects. An additional 14 subjects will be enrolled in order to provide more data for the implant success and survival calculations, thereby bringing the total sample size to 52.

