5.3 Secondary Analysis

If the null hypothesis for the primary analysis is rejected with a one-sided 5% significance level, an additional secondary analysis will be performed testing superiority, where the superiority margin is $-\delta$. The null hypothesis for the secondary analysis is that the difference between the mean change in crestal bone levels for the treatment and control groups is at most the superiority margin (indicating non-superior bone gain). Rejection of the null hypothesis indicates the observed data supports the alternative hypothesis that the difference between the mean change in crestal bone levels for the treatment and control groups is greater than the superiority margin (indicating superior bone gain). The hypotheses associated with the secondary analysis are defined as:

- $H_0: \mu_c - \mu_s \leq -\delta$
- $H_1: \mu_c - \mu_s > -\delta$

where μ_c , μ_s , and δ are defined as above. The hypotheses will be tested using a one-sided t-test with a 5% significance level.

6 Analysis of Secondary Effectiveness Endpoints

All secondary effectiveness endpoints will be summarized descriptively without hypothesis testing.

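### SAP 5, 5.2 and 5.3 use conflicting signs for the primary bone-level endpoint, and the 5.3 step is not a superiority test under either sign

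*SAP*

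**What the plan says.** SAP 5 defines change as the 12-month value minus the loading value, and says the "difference is defined as the change for the treatment group minus the control group". It then sets the descriptive categories: "The mean change in crestal bone levels will also be categorized as Gain (>0), No change (0"), followed by bands of loss.

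SAP 5.2 tests H0: μc − μs ≥ δ against H1: μc − μs < δ, with μc the treatment mean, μs the control mean and δ = 0.5 mm. In words, the null is that the difference between the treatment and "control groups is at least the non-inferiority margin (indicating inferior bone gain").

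SAP 5.3 applies if 5.2 rejects. It sets the superiority margin at −δ and tests H0: μc − μs ≤ −δ against H1: μc − μs > −δ with the same symbols. Its alternative is that the difference "is greater than the superiority margin (indicating superior bone gain").

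Protocol 8.1 has the same non-inferiority inequality as SAP 5.2. For the follow-on step it says only that "a one-side superiority test will be performed at significance level of 5"%, without hypotheses or a margin.

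On measurement, Protocol 5.2.6 says: "Additional details will be provided in operations manual to describe how the central radiologist will measure the bone level values from the radiographs". SAP 1 gives the SAP precedence over the protocol where they differ, and SAP 2.4 ties study success to the primary comparison.

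**The concern.** The direction of the primary test depends on whether a larger bone level means more bone or less, and neither document says so. SAP 5.2 and 5.3 stand next to each other, share their symbols and point in opposite directions, so at least one is wrong whatever the reader's convention. SAP 5.2 decides study success. If it is programmed with positive change as gain, as the category label in SAP 5 suggests, it protects against the test arm being too good instead of too poor. SAP 5.3 would attach the word superior to a result that shows no advantage. SAP 2.1 reports that 46 subjects have already completed the 12-month follow-up, so a sign chosen at the programming stage could look data-driven.

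**Working it through.** **Inputs.** Margin 0.5 mm, SD 0.5 mm in both arms, expected difference 0, one-sided 5% t-test, at least 80% power (SAP 5.1). 46 completers at 12 months (SAP 2.1). The split by arm is not given; 23 per arm is assumed from the 1:1 allocation. D is the true test-minus-control difference in mean change.

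**The plan's own figure.** The power of the non-inferiority t-test at D = 0, from the noncentral t distribution, is 0.797 with 13 per arm and 0.824 with 14. The stated 14 per arm is reproduced. It is the same for either direction of the inequality, so it does not settle the sign.

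**What each section means under each sign.**

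| Section | Gain positive | Loss positive |
|---|---|---|
| SAP 5, positive change is gain | Correct | Wrong |
| SAP 5.2, H1: D < +0.5 | Reversed: shows only that test is not better by 0.5 mm or more | Correct non-inferiority test |
| SAP 5.3, H1: D > −0.5 | The real non-inferiority test, labelled superior | Shows only that test is not better by 0.5 mm or more, labelled superior |

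Under both signs, rejecting both nulls shows −0.5 < D < +0.5 mm. That is the two one-sided tests procedure for equivalence.

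**Operating characteristics with 23 per arm.** SE = 0.5 × √(2/23) = 0.147 mm, df = 44, critical t = 1.680.

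*SAP 5.2 alone, gain-positive coding.* P(reject) = P(T > 1.680), with T noncentral t on 44 df and noncentrality (0.5 − D)/0.147:

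| True D (gain positive) | P(5.2 declares non-inferiority) |
|---|---|
| −0.5 mm (test worse by the margin) | > 0.999 (should be 0.05) |
| 0 | 0.955 |
| +0.1 mm | 0.85 |
| +0.25 mm | 0.51 |
| +0.5 mm (test better) | 0.05 |

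The reversed test therefore fails a better test arm more often than not only once the advantage exceeds about 0.25 mm.

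*SAP 5.2 then 5.3, either sign.* Both reject when the observed difference lies within ±(0.5 − 1.680 × s × √(2/23)), with s the pooled SD. Integrating over the chi-square distribution of s:

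| True difference | 5.2 then 5.3 as written | Superiority test against 0 |
|---|---|---|
| 0 | 0.91 | 0.05 |
| Test better by 0.25 mm | 0.51 | 0.51 |
| Test better by 0.5 mm | 0.05 | 0.955 |

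The joint probability is symmetric in D, so it does not depend on the sign convention.

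*Sensitivity of the joint result at D = 0:* 0.99 at SD 0.4 mm, 0.745 at SD 0.6, 0.34 at SD 0.8, and 0.90 with a 20/26 split at SD 0.5.

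**The case against.** The strongest reply is that the alarm over study success is conditional. Only 5.2 decides success, and it is wrong only if gain is positive. The neighbouring loss bands in SAP 5 are magnitudes, so the >0 beside gain could also be a magnitude. On that reading SAP 5, SAP 5.2 and Protocol 8.1 agree under loss positive, and the error is confined to 5.3. This stands in part: the 0.999 figure is a worst case for one convention. But an undefined sign leaves that case open, and 5.3 is wrong under both.

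Protocol 7.3.4 does not settle the sign. Its "marginal bone level change for Straumann implants was -0.56 mm" comes from a cited meta-analysis, and its instruction to "flag any bone level changes that are greater than 2.5 mm in the first year post-loading" sits under bone-loss reporting and reads naturally as a magnitude. Nor does SAP precedence bear on 5.2, which has the same inequality as Protocol 8.1; it matters for 5.3. Both points are fair, and neither removes the conflict.

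A third reply is that SAP 5.3 explicitly names a margin of −δ. With loss positive, that margin is on the favourable side and only the inequality is misdirected. A correctly directed test against that margin would also reject only 5% of the time at a true 0.5 mm advantage. This is right, so the 0.05 figure does not by itself separate the flawed test from a correct margin test. The behaviour at no difference does: a correctly directed margin test would reject with probability below 0.001, against 0.91 for the sequence as written.

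Finally, the 0.91 depends on the SD and falls to 0.34 at 0.8 mm. Even that is far above the nominal 5%.

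**Conclusion.** The concern holds. SAP 5.2 and 5.3 contradict each other in direction, and nothing elsewhere in the documents repairs this. Under either sign the planned sequence is an equivalence test whose final step is labelled superiority. In the plan's own expected case of no difference, it would declare superiority in about nine trials in ten (0.91, assuming 23 per arm and SD 0.5 mm; 0.34 to 0.99 for SDs from 0.8 down to 0.4 mm).

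Whether 5.2 is itself reversed depends on a sign the documents do not state. If gain is positive it is, and a test arm worse by the full margin would be declared non-inferior almost surely. If loss is positive, 5.2 and Protocol 8.1 are sound. This must be corrected before the primary analysis because it concerns the study-success rule.

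**What to change.** In an amended SAP approved before the primary analysis, as SAP 10.6 provides, state whether a larger value from the central reader means more bone or less, and align the three sections with D = μc − μs.

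- **Gain positive.** 5.2: H0: D ≤ −0.5 against H1: D > −0.5 mm (lower limit of the two-sided 90% CI above −0.5 mm). 5.3: H0: D ≤ 0 against H1: D > 0. SAP 5 stays. The inequality in Protocol 8.1 is reversed at the next amendment.
- **Loss positive.** 5.2 stays (upper limit of the two-sided 90% CI below +0.5 mm). 5.3: H0: D ≥ 0 against H1: D < 0. The gain category in SAP 5 becomes change below 0. Protocol 8.1 needs only the sign of change defined.

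A null of 0 for superiority fits Protocol 8.1, which names no superiority margin. If a 0.5 mm superiority margin is really intended, replace 0 in 5.3 with +0.5 (gain positive) or −0.5 (loss positive) and keep the directions above.

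The cost is SAP wording and a few lines of code, with no effect on subjects, data or sample size (14 per arm still gives power 0.82). Only the gain-positive case needs a corrected protocol inequality, with IRB review under Protocol 10.5; until then the SAP governs under SAP 1.
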